**Screening Procedures**

All patients receiving parenteral nutrition for short bowel disorders at CH&MC are followed by the Department of Surgery as primary or through consults. Eligibility for the trial will be discussed on rounds. Prior historical and physical information, imaging studies, biopsies, and other available specialized tests will be reviewed by the multidisciplinary team experienced in the diagnosis and treatment of parenteral nutrition associated liver disease. Additional biochemical monitoring will be performed as necessary. If the patient's status supports consideration of treatment, the option for experimental therapy will be investigated. A similar process will be utilized for self-referrals and potential patients referred from distant healthcare facilities and will be implemented once they have been transferred to our institution.

**C. Description of Study Treatment**

Bottles containing 50mL or 100 mL of 10% Omegaven® will be purchased from International

[name], Department of Surgery, Children's Hospital & Medical Center  
[name], Department of Surgery, Children's Hospital & Medical Center  
[name], Pediatric Research Office, Dept. of Pediatrics, UNMC  
[name], Department of Biostatistics, College of Public Health, UNMC

Pharmacy of Hamburg, Germany or directly from the manufacturer. FDA Approval is pending to allow for billing of Omegaven®. In the event that third party coverage is not available Children's Hospital & Medical Center will cover all Omegaven® drug costs for patients enrolled in this protocol. Omegaven® is manufactured by Fresenius Kabi AG, Bad Homburg v.d.h, Germany. Omegaven® is formulated as an emulsion from fish oils.

While inpatient, the emulsion for all patients will be repacked into syringes to allow for administration via syringe pump. If patients are to be discharged home on Omegaven®, all doses will be administered from the original manufacturer's container. All study materials will be stored securely until the time of administration. The bottles will be stored at room temperature below 30° C (do not freeze). Damaged or suspect drug will be returned unused to Fresenius-Kabi. Containers should be shaken before use.

All supplies for the study will be accompanied by accountability and shipping documents and will be maintained by the Investigator or deputy (e.g. research pharmacist). Information recorded on these accountability and shipping documents will include relevant dates, batch numbers, quantities received or dispensed, to whom dispensed, returned drug and drug lost or damaged. At the end of the study, all used and unused Omegaven® will be accounted for. If expired, the remaining drug supplies will be destroyed.

#### Details of Omegaven® Administration

After baseline labs are obtained (Tables 2 and 3), therapy with Omegaven® will be initiated at the goal dose of 1 gram /kg/day and infused over 8-24 hours, so long as the infusion rate does not exceed 0.15g/kg/hour. Omegaven® will be infused intravenously through either a central or peripheral catheter alone or in conjunction with parenteral nutrition. If additional fat calories are needed, they will be provided via the enteral route. The same standards of care provided to all patients receiving parenteral nutrition solution will be followed. Routine nutritional monitoring is described in Table 3.

In the event that a patient is unable to achieve adequate calories parenterally and is unable to tolerate enteral feeds, it may be necessary to evaluate whether or not the patient should continue the study with Omegaven® as monotherapy or resume therapy with conventional fat emulsions so that additional parenteral fat calories can be given. The clinical team, in conjunction with the patient's primary physician, will determine if the patient should be removed from the protocol. The DSMB will also be notified.

Orders for Omegaven® will be entered in Epic and must contain the following data elements:

- Total daily dose to be administered in mL
  - The hourly infusion rate (total daily dose ÷ the number of hours to be infused)
- Prior to the administration of each Omegaven® dose, two nurses will check the dose dispensed against the physician's orders and verify that the infusion pump settings (hourly rate, volume to be infused) are correct before the infusion is started.

As previously mentioned, Omegaven® may be infused in the same manner as conventional fat emulsions through either a central or peripheral line. The emulsion is isotonic. It is compatible with parenteral nutrition solutions and may be co-infused via y-site. Per Infection Control, source containers must be changed every 12 hours and unused product discarded. Omegaven® may be infused through a 1.2micron inline filter.

[name], Department of Surgery, Children's Hospital & Medical Center  
[name], Department of Surgery, Children's Hospital & Medical Center  
[name], Pediatric Research Office, Dept. of Pediatrics, UNMC  
[name], Department of Biostatistics, College of Public Health, UNMC

### Dose Modification

#### Lipid Intolerance

If lipid intolerance develops, defined as serum triglyceride levels > 200 mg/dL, the following will be considered prior to reducing the dose:

- a) If the level was obtained while the patient was receiving a continuous 24-hour infusion of Omegaven®, the total dose should be infused over 20 hours, and a repeat serum triglyceride level obtained prior to resuming the infusion 4 hours later.
- b) Other sources of lipid intolerance should be considered and addressed (drugs, renal disease)

If the triglycerides continue to remain high despite the aforementioned interventions, a dosage reduction of 25% of the current dose will be considered.

### Duration of Therapy

Patients will remain on Omegaven® until weaned from PN. Patients may continue monotherapy with Omegaven® as an additional source of calories after the dextrose/protein portion of PN is discontinued.

In the event that a patient who has been listed for a liver or liver/intestinal transplant has an organ become available, the participation in this protocol will not preclude them from receiving the transplant.

### Disruption of Therapy

In event that Omegaven® cannot be administered (i.e. loss of central venous catheter access, fluid restrictions, need to administer an incompatible medication/blood product), the infusion of Omegaven® may be interrupted and resumed when the conflicting situation is resolved. Some potential interventions that can be used include:

Situation	Possible Solution
Loss of central venous access	Administer via peripheral route
Fluid restriction	Consult with pharmacy to concentrate PN, medications to allow for administration
Limited access, need to administer incompatible medications	Stop Omegaven® infusion, flush catheter with either NS or dextrose, administer incompatible medication, flush catheter, resume infusion; may be necessary to infuse Omegaven® over 8 -24 hours. Multiple syringes should be used so as to keep maximum hang time of Omegaven® source container less than 12 hours) Regardless of the infusion time, the infusion rate cannot exceed 0.15g/kg/hour.

### Discontinuation of Therapy

Patients will continue to be followed by the Department of Surgery upon discontinuation of therapy with Omegaven® for a minimum of 2 months after the treatment is stopped.

[name], Department of Surgery, Children's Hospital & Medical Center  
[name], Department of Surgery, Children's Hospital & Medical Center  
[name], Pediatric Research Office, Dept. of Pediatrics, UNMC  
[name], Department of Biostatistics, College of Public Health, UNMC

### Resumption of Therapy

For patients who have been off the protocol more than 1 year, in the event that the patient must receive intravenous fat emulsion, treatment with Omegaven® will resume only if the patient shows evidence of PN liver damage (elevations in direct bilirubin  $\geq 2$  or pathology findings consistent with cholestasis). Otherwise, the patient will be treated with conventional fat emulsion.

### **D. Definition of Primary and Secondary Outcomes/Endpoints**

Generally, primary safety analyses will be based on time from baseline or 30 days after baseline until two months after patients first reached direct bilirubin levels  $< 2$  mg/dL. Baseline will be defined as information collected at the date that treatment starts for Omegaven® patients and on the date that patient reached bilirubin levels  $> 2$  for soybean oil fat emulsion patients. Information on mortality and transplant will be collected during the whole treatment with Omegaven®. Primary efficacy analysis will include time from baseline until the patient normalizes bilirubin (presents three consecutive direct bilirubin  $\leq 2$  mg/dL or a direct bilirubin  $\leq 2$  mg/dL and weaned from TPN).

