#### Hypothesis for Aim 1:

1.1 – After starting Omegaven® on PN, the rate of fatty acid deficiencies and imbalances will be as low as before Omegaven®. Also, the rate of triglyceride events > 400 mg/dL with Omegaven® will be similar to that seen with PN administered with soy oil IFE (conventional emulsion, i.e., Intralipid®).

1.2 – PN containing Omegaven® will be safe for patients with respect to the risk of unexpected bleeding, coagulopathies, and other adverse events.

[name], Department of Surgery, Children's Hospital & Medical Center  
[name], Department of Surgery, Children's Hospital & Medical Center  
[name], Pediatric Research Office, Dept. of Pediatrics, UNMC  
[name], Department of Biostatistics, College of Public Health, UNMC

1.3 – PN containing Omegaven® will promote more short-term growth and development than conventional fat emulsions.

2. To determine if established PN associated liver disease can be reversed or its progression halted by using a parenteral fat emulsion prepared from fish oil as measured by normalization of serum levels of hepatic enzymes and bilirubin.

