**Hypothesis for Aim 2:**

2.1 – Our primary hypothesis is that, after reaching bilirubin levels  $> 2$  mg/dL, patients receiving Omegaven® will reach a bilirubin level  $\leq 2$  mg/dL faster than patients receiving conventional fat emulsions. Additionally, while patients receiving Omegaven® will experience a decrease in their levels of bilirubin and other hepatic enzymes over time, patients receiving conventional emulsions will maintain high levels of bilirubin and other hepatic enzymes over time.

2.2 – Patients with surgical gastrointestinal disease and cholestasis will have better clinical hepatic outcomes than patients receiving conventional emulsions.

2.3 – Since patients receiving Omegaven® will have improved immune function, they will have a lower infection rate than patients receiving conventional fat emulsions.

2.4 – Due to a better general hepatic condition, patients receiving Omegaven® will also experience lower occurrence of liver transplant, death from hepatic associated causes, and blood transfusions.

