## **DESIGN AND METHODS**

### **A. Study Design**

Assessment of the effect of treatment will be based on a non-randomized, open-labeled, prospective study of intravenously administered Omegaven® fat emulsion to determine safety and preliminary efficacy in the treatment of PN associated liver injury.

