**Inclusion Criteria:**

1. Patients will be PN dependent (unable to meet nutritional needs solely by enteral nutrition) and are expected to require PN for at least another 30 days.
2. Patients considered eligible for study participation must have parenteral nutrition associated liver disease (PNALD) as defined as a direct bilirubin of  $\geq 2$  mg/dl on at least the last two consecutive measures or by histology and/or currently on Omegaven through another protocol and unable to remain on that protocol due to transfer to our institution. Other causes of liver disease should be excluded. A liver biopsy is not necessary for treatment.
3. The patient must have utilized standard therapies to prevent the progression of his/her liver disease including surgical treatment, cyclic PN, avoiding overfeeding, reduction/removal of copper and manganese from PN, advancement of enteral feeding, and the use of ursodiol (i.e., Actigall®).
4. Patients ages birth up to and including 18 years of age.

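### Hypotheses 1.3 and 2.1 to 2.4 claim superiority over conventional emulsion, but the protocol defines, treats and follows Omegaven patients only

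*Protocol*

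**What the plan says.** **Hypotheses.** Under Hypothesis for Aim 2, 2.1 is labelled primary and says Omegaven patients will reach a bilirubin of 2 or below "mg/dL faster than patients receiving conventional fat emulsions". Hypothesis 2.2 says patients with surgical gastrointestinal disease and cholestasis "will have better clinical hepatic outcomes than patients receiving conventional emulsions"; it does not name Omegaven, although that is evidently meant. Hypothesis 2.3 says "they will have a lower infection rate than patients receiving conventional fat emulsions". Hypothesis 2.4 says Omegaven patients "will also experience lower occurrence of liver transplant, death from hepatic associated causes, and blood transfusions", without saying lower than whom. Under Hypothesis for Aim 1, 1.3 says "PN containing Omegaven® will promote more short-term growth and development than conventional fat emulsions"; it names emulsions, not patients.

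**Design.** Section A describes a "non-randomized, open-labeled, prospective study of intravenously administered Omegaven® fat emulsion to determine safety and preliminary efficacy". Section B sets out one population, and Details of Omegaven Administration starts Omegaven once baseline laboratory tests are done. Section E names no comparator records.

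**Baseline.** Section D gives two rules: "Baseline will be defined as information collected at the date that treatment starts for Omegaven® patients and on the date that patient reached bilirubin levels" above 2, the second being for patients on soybean-oil emulsion. Analysis of Baseline Characteristics gives only one, the last value before Omegaven.

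**Analysis.** Analysis of Efficacy plans Kaplan-Meier curves, Cox hazard ratios adjusted for baseline confounders, a comparison of mean and maximum modified PELD scores, and a logrank and Cox comparison of infection rates. None of these states which groups are contrasted.

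**The concern.** A claim of faster, better, lower or more needs something to be compared with. Who supplies the comparison is a design element: it decides whom to identify, whose records to abstract and when follow-up starts. It cannot be left to an analysis plan, because an analysis plan cannot create a cohort that the protocol never sets up.

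The orphan baseline in Section D makes this more than loose wording. It is an operative rule for a group that does not exist elsewhere, and it does not fit the Omegaven-only baseline in the analysis section. An analyst handed this protocol could not tell whether a control cohort is expected, nor what the hazard ratios and the logrank test are meant to contrast. At stake is whether the labelled primary hypothesis of Aim 2 can be addressed at all.

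**Working it through.** The protocol gives no figure for this comparison, so the check sets sections side by side.

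**Step 1. Is a conventional-emulsion group defined anywhere?**

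- Section A: a study of Omegaven; no second group.
- Section B: one set of eligibility criteria, for patients who will receive Omegaven.
- Section C: every enrolled patient starts Omegaven. The mention of conventional emulsion under Resumption of Therapy is a re-treatment rule for patients off protocol for more than a year, not a control group.
- Section E: chart review of clinical history; no historical cohort named.
- Data Analysis Plan: under intention to treat, each patient counts as receiving Omegaven throughout follow-up.
- Statistical Power and Sample Considerations: enrolment follows compassionate use. Table 4 covers 20, 25 or 30 patients in one group, before versus after Omegaven (McNemar). No control-group size is given.

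Result: conventional-emulsion patients defined, none.

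**Step 2. Can each patient serve as his or her own control?** This depends on how the outcomes are counted.

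| Hypothesis | Outcome | Where counting starts | Pre-Omegaven counterpart defined? |
|---|---|---|---|
| 2.1, 2.2 | Time to bilirubin normalisation | Baseline (Section D; Analysis of Efficacy) | No |
| 2.3 | Bloodstream infections per follow-up time on PN | After baseline (Outcome/Endpoints) | No |
| 2.4 | Death, transplant | During Omegaven treatment (Section D) | No |
| 1.3 | Change in weight and height Z-scores | Forward from baseline (Analysis of Safety and Tolerability) | No |

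Adverse events are likewise assessed from the first Omegaven infusion (Section G). Hypothesis 1.3, which names emulsions and not patients, could be read within patient, but the growth analysis as defined offers no earlier period to set against it.

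**Step 3. What is left without a contrast?** Four items: the soybean-oil baseline (Section D), the confounder-adjusted hazard ratios, the PELD comparison, and the logrank comparison of infection rates (all three under Analysis of Efficacy). A hazard ratio adjusted for confounders presupposes an exposure contrast. In a cohort where everyone is exposed, the Cox model can describe only prognostic factors.

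**Step 4. What remains supported?** The Kaplan-Meier estimate of time to normalisation, individual profiles from 2 months before baseline, trends in liver markers, and the paired pre/post safety comparisons need no second group. The triglyceride clause of 1.1 also refers to soy-oil emulsion and can be met within patient where earlier values exist. They may not exist for patients entering under the criterion "or by histology and/or currently on Omegaven through another protocol".

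**Step 5. What precision would single-arm estimates have?** The protocol states no expected rate, so the results are assumed over a range and n is taken from Table 4. Limits are exact (Clopper-Pearson) 95%: lower = Beta quantile at 0.025 with parameters x and n − x + 1; upper = Beta quantile at 0.975 with parameters x + 1 and n − x.

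| Assumed proportion normalising | n = 20 | n = 30 |
|---|---|---|
| 50% | 10/20: 27 to 73% | 15/30: 31 to 69% |
| 70% | 14/20: 46 to 88% | 21/30: 51 to 85% |
| 90% | 18/20: 68 to 99% | 27/30: 73 to 98% |

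With no deaths or transplants, the upper limit is 1 − 0.025^(1/n): 1 − 0.025^(1/20) = 16.8% and 1 − 0.025^(1/30) = 11.6%.

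**The case against.** The best defence is that the single-treatment design is open and deliberate. Efficacy is called preliminary, enrolment follows compassionate use, the primary safety analysis is descriptive, and the protocol says treatment is for patients without a suitable standard therapy. No enrolment, dosing, withdrawal or monitoring rule depends on the comparative clauses, and the study ends on outside events (Section F). On that view the repair is largely one of wording.

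Much of this stands, and it limits the harm to the comparative claims. It does not remove the problem: 2.1 is labelled primary, and Section D contains a working rule for a group that the rest of the protocol does not have.

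A second defence is that chart review under Section E could supply historical controls or earlier within-patient data. It could, but the protocol does not say so, and the outcomes for 1.3 and 2.1 to 2.4 are defined forward only. Liver-marker profiles do reach back 2 months before baseline, but they are descriptive and give no earlier counterpart to time to normalisation.

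A reader might infer that the differing start dates in Section D would produce a falsely favourable hazard ratio for Omegaven. The documents do not support that. There is no control group to bias, and they give neither the gap between crossing the threshold and starting treatment nor the shape of the natural history. Neither size nor direction can be stated.

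**Conclusion.** The point holds on the text and should be corrected. Five hypotheses (1.3, 2.1, 2.2, 2.3 and 2.4) make or imply a comparison with conventional emulsion for which no comparator is defined and no counterpart outcome collected. Hypothesis 1.1 also compares, but its triglyceride clause can be met within patient and is not part of this point.

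The conclusion rests on no numerical assumption. It assumes only that a comparator cohort belongs in the protocol, so that an unseen analysis plan would not cure its absence.

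Two stronger readings should be resisted. One is that the efficacy part is worthless: the study can still report how often and how fast Omegaven patients normalise. The other is that the sponsor means to choose a control group after seeing results: the leftover wording leaves that open but gives no evidence of it.

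**What to change.** Amend the protocol as follows.

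- Restate 1.3 and 2.1 to 2.4 as single-arm estimates or changes from baseline, with confidence intervals, and name Omegaven in 2.2.
- Delete the soybean-oil baseline from Section D, so that it agrees with Analysis of Baseline Characteristics.
- Under Analysis of Efficacy, limit the Cox models to prognostic factors within the cohort. Replace the logrank comparison with the infection rates already defined under Outcome/Endpoints, and the PELD comparison with PELD summaries, each with intervals.
- Keep the triglyceride clause of 1.1 as a within-patient before/after comparison, for patients with pre-Omegaven values.

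If a historical control is truly intended, declare its source and eligibility in Section A. Use one common time zero for both groups, because Section D now starts one clock at a bilirubin crossing and the other at treatment.

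**Cost.** The first route needs an amendment, with DSMB review of it (amendments are within its listed responsibilities), and no new patients, visits or tests. The comparative efficacy claim is given up and, as shown above, intervals are wide at 20 to 30 patients. The historical-control route costs more, since a cohort must be identified, selected and abstracted.

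### The efficacy clock starts at first dose for Omegaven children but at bilirubin above 2 for soybean-oil children, so the comparison in hypothesis 2.1, if made under that rule, is in general misaligned

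*Protocol*

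**What the plan says.** Section D (Definition of Primary and Secondary Outcomes/Endpoints) gives two baselines in one sentence: "Baseline will be defined as information collected at the date that treatment starts for Omegaven® patients and on the date that patient reached bilirubin levels" above 2 "for soybean oil fat emulsion patients". It then ties the endpoint to that baseline: "Primary efficacy analysis will include time from baseline until the patient normalizes bilirubin".

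Hypothesis 2.1, named as the primary hypothesis for Aim 2, has a single starting condition: "Our primary hypothesis is that, after reaching bilirubin levels" above 2 mg/dL, Omegaven patients are expected to come down to 2 mg/dL or less "faster than patients receiving conventional fat emulsions".

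Inclusion criterion 2 requires direct bilirubin of at least 2 mg/dL "on at least the last two consecutive measures or by histology and/or currently on Omegaven through another protocol", the last being children who cannot stay on that protocol because of transfer. Criterion 3 adds: "The patient must have utilized standard therapies to prevent the progression of his/her liver disease".

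The Data Analysis Plan defines baseline only for Omegaven, as the last measurement before it is started. Its efficacy section plans Kaplan-Meier curves and Cox hazard ratios adjusted for baseline confounders. It gives an infinite time to children who die or are transplanted before normalising. It mentions no delayed entry, time-varying treatment or other alignment of the time origin. The Study Design section describes no soybean cohort.

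**The concern.** A claim that one group normalises faster needs the same starting point in both groups. Under section D it is not the same. A soybean child is on the clock from the day bilirubin passes 2, with no confirmatory value stated. An Omegaven child entering by the bilirubin route is on the clock only from first dose, after a second qualifying value, evaluation and consent, and only if still alive, not transplanted and not recovered.

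Early recoveries, deaths and transplants in that interval can therefore appear in the soybean group but not among these Omegaven children. Adjusting for baseline covariates in a Cox model does not repair a shifted origin. At stake is whether a difference in time to normalisation could be read as a drug effect at all.

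**Working it through.** The protocol gives no event count, hazard ratio or power for this endpoint, so there is no figure of its own to reproduce. The check has two parts.

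**1. The texts side by side**

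| Place | Omegaven clock starts | Soybean clock starts |
|---|---|---|
| Section D | first dose | bilirubin above 2 (direct or total not stated) |
| Hypothesis 2.1 | after bilirubin above 2 | after bilirubin above 2 |
| Analysis of Baseline Characteristics | last value before Omegaven | not defined |

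**2. Size under no drug effect**

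Assumptions, none of them in the documents: both groups share one natural course; time from first value above 2 to normalisation is Weibull with shape s and median M = 120 days; Omegaven starts after a lag L of 14, 30 or 60 days in children not yet normalised; death and transplant are ignored.

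The survival function is S(t) = exp(−ln2 · (t/M)^s). The soybean median is M. The Omegaven median from first dose, r, solves S(L + r)/S(L) = 1/2, so

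r = (M^s + L^s)^(1/s) − L.

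Example, s = 2 and L = 30: √(14400 + 900) − 30 = 123.7 − 30 = 93.7 days, and 93.7/120 = 0.78, about 22% shorter.

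| Shape s | L = 14 | L = 30 | L = 60 | Change from 120 days |
|---|---|---|---|---|
| 2 (rising hazard) | 106.8 | 93.7 | 74.2 | 11% to 38% shorter |
| 1.5 (rising hazard) | 109.2 | 99.8 | 86.8 | 9% to 28% shorter |
| 1 (constant) | 120 | 120 | 120 | none |
| 0.7 (falling hazard) | 145.8 | 159.9 | 178.1 | 22% to 48% longer |

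A shorter lag gives a smaller shift. The lab schedule for treated children with direct bilirubin of 2 or more is weekly, so two values could be about 7 days apart. At L = 7 the same formula gives 5-6% shorter (s = 1.5 to 2) or 14% longer (s = 0.7).

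A separate simulation looked at the Cox hazard ratio for normalisation, with true ratio 1, an assumed 12-week median and censoring at 52 weeks:

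| Shape s | Lag 1 wk | 2 wk | 4 wk | 8 wk |
|---|---|---|---|---|
| 2 | 1.11 | 1.24 | 1.54 | 2.18 |
| 1.5 | 1.06 | 1.14 | 1.27 | 1.45 |
| 1 | 0.99 | 1.00 | 1.01 | 1.00 |
| 0.7 | 0.91 | 0.88 | 0.84 | 0.78 |

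The constant-hazard case also needs children to be alike. With a constant hazard within each child but gamma-distributed variation between children (shape 1), a 4-week lag moved the no-effect median from 12.0 to 16.0 weeks.

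**The case against.** The strongest reply is that the study is in effect single-arm. The design section describes only Omegaven treatment, the intention-to-treat definition speaks only of Omegaven, the safety comparisons are before and after in the same children, and the efficacy section mentions hazard ratios without naming groups. The soybean comparison appears only in the hypotheses and one clause of section D. This stands as a limit: if no soybean group is analysed, first dose is an ordinary and consistent origin, and only wording needs repair. It does not remove the point, because section D still writes a baseline rule for soybean patients and 2.1 still makes a between-group claim.

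Hypothesis 2.1 can also be read as describing the population, cholestatic children, rather than fixing a clock. That is possible, but a claim about speed still needs one origin.

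A reader might infer that any such comparison must be biased, and in favour of Omegaven. The documents do not support this. A constant, homogeneous hazard gives no bias, and other courses give either sign. Leaving early deaths out of the Omegaven group flatters it; leaving early recoveries out does the reverse. The calculation omits the rule giving deaths and transplants infinite time, so its range is illustrative.

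Nor does every Omegaven child wait through two values. Histology entrants need not, and children already treated under another protocol may have had their first dose before enrolment; which date is then their baseline is not stated. Criterion 3 need not add lag either, since standard therapies may have been in place before bilirubin rose.

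**Conclusion.** The point holds as an internal inconsistency with a conditional consequence. Section D fixes two time origins, hypothesis 2.1 compares the groups from one condition, and the analysis plan defines baseline for Omegaven alone. If the soybean comparison is made as section D directs, it is in general biased with no drug effect, and nothing in the stated analysis corrects it.

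Direction and size cannot be settled from the documents. With the assumed 120-day median, a 14 to 60 day lag, and no deaths or transplants, the Omegaven median is about 9-38% shorter under a rising hazard (shape 1.5 to 2), about 22-48% longer under a falling one (shape 0.7), and unchanged under a constant one. It would go too far to say that a planned primary contrast is already known to be biased, because the efficacy section never sets that contrast up. The rule should still be corrected, since it bears on what the primary efficacy hypothesis can support, in an analysis the protocol itself calls preliminary.

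**What to change.** Choose one of two courses.

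- **(a) A soybean comparison is kept.** Use one eligibility-based time zero for both groups, for example the date on which the liver disease criterion of inclusion item 2 is first met, by bilirubin or histology. Let Omegaven children join the risk set at first dose (delayed entry), or model treatment as time-varying. Analyse children transferred while already on Omegaven separately, or leave them out of this contrast. Moving the Omegaven clock back without delayed entry is not enough, because it adds time in which the child could not have had the event. In the simulation with a 12-week median and a 4-week lag, the no-effect Omegaven median became 12.7 weeks (shape 2), 16.0 (constant hazard) or 20.8 (shape 0.7).
- **(b) No soybean group is analysed.** Delete the soybean baseline from section D and restate 2.1 as time from first Omegaven dose, with no claim of being faster than another group.

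In either case, record the date of the first direct bilirubin above 2 mg/dL where available, and report the interval from it to first dose.

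The cost is one extra chart date per child and the protocol wording, plus a slightly more complex survival model under (a). Section E already provides for chart review, and the efficacy section already plans individual profiles starting two months before baseline or at birth.
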